- 638639 The BGM group will be instructed on how to optimally use SMBG for diabetes management.
- 640
- 641 Further details on instructions to each group are provided in section 5.1.
- 642
- 643
- 644

645 CHAPTER 5: RANDOMIZED TRIAL PHASE

646

647 **5.1 Home Procedures and Diabetes Management**

648 **5.1.1 CGM Group**

Each participant will be asked to use a CGM sensor on a daily basis, inserting a new sensor as needed.
Participants will be instructed to use the sensor according to FDA labeling. In addition, participants will be advised to check the blood glucose when symptoms or expectations do not match the CGM reading.

652

653 Participants in the CGM group will be encouraged to view retrospective CGM data weekly on a home 654 computer or the smartphone application if it is being used.

655

656 **5.1.2 BGM Group**

A study blood glucose meter and test strips will be provided and will be used for a fingerstick blood glucose check with a recommendation of 4 times a day. Participants will be permitted to check a fingerstick glucose as many times a day as they choose.

660

661 **5.2 Study Visits and Phone Contacts**

662 CGM Group will have a study visit at 10 days, while the BGM Group will have a phone call for the 10-663 day contact. In-clinic study visits for both groups will occur at 4, 8, 16 and 26 weeks. 664

In addition to the in-clinic study visits, the BGM group will have blinded sensor placement visits one
week prior to each of the 8, 16, and 26 week visits.

668 **5.2.1 Study Visits**

- 669 Study visits for both groups will occur at
 - 10 days (+3 days)
- 671 4 weeks (\pm 7 days)
 - 8 weeks (\pm 7 days)
 - 16 weeks (\pm 7 days)
 - 26 weeks (\pm 7 days)
- 674 675

670

672

673

Blinded sensor placement visits at: 7, 15 and 25 weeks for BGM group.

- 677678 Additional office visits may occur as needed.
- 679

680 **Procedures at Study Visits**

- 681 The following procedures will be performed in both groups at each visit, unless otherwise specified:
- Assessment of compliance with CGM (CGM group) and fingersticks (BGM group)
- Solicitation of the occurrence of adverse events, including falls, hospitalizations, emergency
 department visits, severe hypoglycemia, and diabetic ketoacidosis
- Assessment of device issues
- Skin assessment for CGM group and following blinded sensor wear for BGM group
- Review of glucose data and insulin dosing and recommendations for changes in diabetes
 management
- HbA1c determination using a point of care device or local lab (8, 16, and 26 weeks)
- Collection of a blood sample to send to the central laboratory for HbA1c determination (16 and 26 weeks)
- Completion of questionnaires (26 weeks)

693	 Hypoglycemia Fear Survey 					
694	 Diabetes Distress Scale (DDS) 					
695	 Glucose Monitoring System Satisfaction Survey (GMSS) 					
696	 Patient-Reported Outcomes Measurement Information System (PROMIS) Global Health 					
697	Short Form					
698	 Hypoglycemia Unawareness Assessment –Clarke survey 					
699	 Preferring Hypoglycemia Scale 					
700	 Cost utility questionnaires including EQ-5D-5L and SF-12V2 					
701	 NIH Cognitive Toolbox 					
702	 NIH Emotions Toolbox 					
703						
704	5.2.2 Phone Contacts					
705	A phone contact will be scheduled at the following times:					
706	• 10 days (+ 3 days) – BGM group only					
707						
708	The purpose of the phone contact will be:					
709	• Solicitation of the occurrence of adverse events, including falls, hospitalizations, emergency					
710	department visits, severe hypoglycemia, and diabetic ketoacidosis					
711	Reminder about upcoming study visit					
712	Additional phone contacts may be performed as needed.					
713						
714	5.3 Use of Blinded CGM by BGM Group					
715	A blinded CGM sensor will be placed for the BGM group and worn for 7 days, with instructions to					
716	calibrate using the study provided BGM as indicated by the current sensor labeling.					
717						
718	The blinded sensor will be placed at a separate visit one week prior to each of the 8, 16, and 26-week					
719	study visits.					
720	Destingents will being the CCM to the clinic of the power study wight					
721 722	Participants will bring the CGM to the clinic at the next study visit.					
723	The blinded sensor data will not be viewed by study staff involved in the care of the participant at the 8					
724	and 16 week visits.					
725						
726	At the 26-week visit, sensor wear may be repeated for up to 7 additional days if there are fewer than 96					
727	hours of glucose measurements for the blinded sensor wear between the 25 and 26 week visits. The 26-					
728	week visit will be deferred if blinded sensor wear is repeated.					

729 730	CHAPTER 6: EXTENSION STUDY

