589 4.2 Testing and Assessments

Testing and Assessments will include the following: 590 591

- 1) Cognitive Battery using NIH toolbox
- 2) Emotions Battery using NIH toolbox

594 Prior to the cognitive battery testing, a fingerstick will be performed to ensure the participant is not hypoglycemic. The cognitive testing should be delayed until hypoglycemia is resolved. Randomization 595 596 may be delayed until cognitive testing is completed.

597

604

605

606

598 Questionnaires not completed at screening may be done at the randomization visit prior to randomization 599 on the study website. The questionnaires are described in chapter 7. Instructions for testing administration 600 will be detailed in a procedures manual.

601 602 4.3 Blood Samples

Blood will be drawn and sent to the central lab for: 603

- HbA1c
- C-peptide (nonfasting) + glucose •

607 4.4 Randomization

608 Eligible participants will be randomized to one of two treatment groups in a 1:1 allocation:

- 1. CGM Group
- 2. BGM Group
- 610 611

614

615

609

612 The participant's randomization group assignment is determined by entering the Randomization Visit data on the study website. 613

- The Jaeb Center will construct a Master Randomization List using a permuted block design.
- Randomization will be stratified by clinical site •
- 616

617 4.5 Study Supplies

618 The CGM group will be provided with the newest model of the CGM available at the time of study

619 initiation (a newer model may be provided if one becomes available during the study), inclusive of a receiver, transmitter, and sensors. 620

- 622 One week prior to the 8, 16 and 26 week visits, the BGM group will have a sensor placed and will be
- 623 provided with a professional CGM in blinded mode.
- 624
- 625 All study participants will be provided with a study blood glucose meter and test strips.
- 626

627 **4.6 Initial Management Instructions**

- In both groups, adjustments in insulin management will be made as needed. Data from the blinded wear should not be used for adjustments in diabetes management for participants randomized to the BGM group. Blinded CGM data may only be reviewed following the 26 week outcome visit for the BGM group.
- 632

Both groups will be provided with instruction sheets regarding diabetes management pertinent to theirtreatment group.

- 635636 The CGM group will be instructed on use and care of the CGM and how to use the CGM in real time to637 make management decisions.

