1040 and at 26 weeks was 7% (95% CI 6%, 8%) (100 minutes per day). The standard deviation of the 26-week

1041 time < 70 mg/dL adjusted for correlation with baseline was 4.5% (95% CI 4.0%, 5.0%) (65 minutes per

1042 day). For a conservative estimate the lower end of the BGM group estimate at 26-weeks (6%) and the

1043 upper end of the confidence interval for the standard deviation (5%) was used for sample size selection.

1044 1045

1046

Table 1. Sample Size Estimates for Primary Hypoglycemia Outcome(% of time < 70 mg/dL)	SD	Power	Treatment Relative Reduction			
		33%	50%	66%	
4%	80%	132	58	36	
	85%	150	66	40	
	90%	174	78	48	
4.5%	80%	166	74	44	
	85%	188	84	50	
	90%	220	98	58	
5%	80%	204	90	54	
	85%	232	102	62	
	90%	270	120	72	

1047

From Table 1 above, it can be seen that a sample size of 120 for a 1:1 randomization would have 90% power with a type 1 error rate of 5% (2-tailed) to detect a difference in time <70 mg/dL, assuming the true

- power with a type 1 error rate of 5% (2-tailed) to detect a difference in time < /0 mg/dL, assuming the true treatment effect is a 50% reduction in the time spent <70 mg/dL and the effective standard deviation is 5%.
- 1052

1053 Using the same assumptions, a sample size of 90 would have 80% power for secondary analyses

1054 conducted separately for pump and injection users (without adjusting for multiple comparisons). In order

1055 to accommodate these important secondary analyses and to account for participants with incomplete

1056 follow up, the sample size was selected to be 200 with the goal of having 180 participants complete the

1057 trial. With this sample size the power will be 98% for the primary analysis under the assumptions

- 1058 described above.
- 1059

1060	10.4 Efficacy Endpoints
1061	Drimony Efficiency Endnoint
1062	Primary Efficacy Endpoint
1063	- % time <70 mg/dL
1064	Secondary Efficacy Endpoint
1065	- Hypoglycemia
1066	• $\%$ time <54 mg/dL
1067	• % time $<60 \text{ mg/dL}$
1068	• Rate of CGM measured hypoglycemic events (using <54 mg/dL)
1069	- HbA1c
1070	• change in HbA1c from baseline to 26 weeks
1071	• % with HbA1c $< 7.0\%$
1072	• % with HbA1c $< 7.5\%$
1073	• % with relative reduction $\geq 10\%$
1074	• % with absolute reduction $\geq 0.5\%$
1075	• % with absolute reduction $\geq 1\%$
1076	• % with absolute reduction $\ge 1\%$ or HbA1c $< 7.0\%$
1077	- Glucose Control
1078	• % time in range 70-180 mg/dL
1079	• mean glucose

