- Per-Protocol Analysis Dataset will include only compliant participants. It will be limited to participants who have at least 168 hours of CGM data and will exclude participants in BGM Group who started CGM prior to having 168 hours of blinded CGM data or who averaged fewer than 3 BGM measurements per day, and exclude those in the CGM group who were using CGM less than 5 days we week on average.
- 1124 The primary analysis will follow the intention-to-treat principle. It will include all randomized 1125 participants, the data from whom will be analyzed in the group to which the participants were assigned 1126 through randomization. Available sensor data will be pooled; no minimum amount of CGM data will be 1127 required for inclusion in the analysis.
- 1128

1112

1114

A per-protocol analysis will be performed to provide additional information regarding the magnitude of
treatment effect. The per-protocol analysis will only be performed if at least 10% of randomized
participants would be excluded by these criteria.

1132

1135

1133 The intent-to-treat analysis is considered primary and if the results of the per-protocol analysis and intent-1134 to-treat analysis differ, the per-protocol analysis will be interpreted with caution.

1136 **10.6 Analysis of the Primary Efficacy Endpoint**

Mean ± SD or summary statistics appropriate to the distribution will be given by treatment group for percent of time spent <70 mg/dL. Percent of time <70 mg/dL will be compared between treatment groups by using a linear model adjusting for the baseline value and site as a random effect. A 95% confidence interval will be reported for the difference between the treatment groups based on the linear model. Residual values will be examined for an approximate normal distribution. If values are highly skewed then a transformation or a non-parametric method based on ranks will be used instead.

1143

Inbalances between groups in important covariates are not expected to be of sufficient magnitude to produce confounding. However, the presence of confounding will be evaluated in a sensitivity analysis by including factors potentially associated with the outcome for which there is an imbalance between groups.

1147

1148 **10.7 Analysis of the Secondary Efficacy Endpoints**

1149 *HbA1c*

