 $F:\label{eq:studies} \label{eq:studies} F:\label{eq:studies} F:\label{eq:studies} \label{eq:studies} F:\label{eq:studies} F:\label{eq:studies} \label{eq:studies} F:\label{eq:studies} \label{eq:studies} F:\label{eq:studies} \label{eq:studies} F:\label{eq:studies} \label{eq:studies} F:\label{eq:studies} \label{eq:studies} \label{eq:studies} F:\label{eq:studies} \label{eq:studies} F:\label{eq:studies} \label{eq:studies} \label{eq:studies} F:\label{eq:studies} \label{eq:studies} \label{eq:studies} \label{eq:studies} F:\label{eq:studies} \label{eq:studies} \lab$

158	•	CGM	group:
159		0	Average \geq 5 days per week of CGM use (see section 0 for details of how this is
160			calculated), which equates to >70% compliance with the CGM intervention
161	•	BGM	group:
162		0	Average \geq 3 BGM measurements per day (see section 17.3 for details of how this
163			is calculated)
164		0	Did not initiate non-study CGM before reaching 168 hours of follow-up blinded
165			CGM data
166	Confou	unding	

- 167 Imbalances between groups in important covariates are not expected to be of sufficient
- 168 magnitude to produce confounding. The primary analysis described below will include a pre-
- 169 specified list of covariates. As an additional sensitivity analysis, any baseline demographic or
- 170 clinical characteristics observed to be imbalanced between treatment groups will be added as
- 171 covariates to the analyses of the primary outcome. The determination of a meaningful baseline
- 172 imbalance will be based on clinical judgement and not a p-value.

173 Missing Data

- 174 It is worth emphasizing that any statistical method for handling missing data makes a number of
- 175 untestable assumptions. The goal will be to minimize the amount of missing data in this study so
- 176 that results and conclusions will not be sensitive to which method is used.
- To that end, sensitivity analyses will be performed to explore whether results are similar whenusing different methods. The following methods will be applied:
- Direct likelihood (primary analysis described above)
- Rubin's multiple imputation (sensitivity analysis)
- Available cases only (sensitivity analysis)

182 7. Analysis of the Primary Efficacy Endpoint

The primary outcome will be a treatment group comparison of the percentage of sensor values in
the hypoglycemic range (<70 mg/dL) adjusted for baseline.

185 7.1. Included Subjects

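### Separate pump and injection analyses are planned and partly set the sample size, but no treatment-by-delivery-method interaction test is planned and the primary model omits the factor

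*Protocol*

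**What the plan says.** **Where delivery method matters to the plan.** Protocol 1.5.4, 2.1 and 2.3.1 set a minimum of 40% pump users and 40% injection users. In 10.3, 120 participants already give 90% power for the primary comparison, and 90 give 80% power in each delivery-method group, without multiplicity adjustment. The total of 200, with 180 expected to complete, was chosen "to accommodate these important secondary analyses and to account for participants with incomplete" follow-up. Section 10.17 repeats all primary and secondary outcomes, and the count of severe hypoglycemic events, separately in pump and injection users.

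**Where it is absent.**
- Protocol 4.4: "Randomization will be stratified by clinical site". No second factor is named.
- Protocol 10.6: the primary outcome is compared "by using a linear model adjusting for the baseline value and site as a random effect". Imbalanced factors may be added in a sensitivity analysis.
- Protocol 10.14: eleven baseline factors are listed for treatment-by-factor interaction, down to cognitive scores and C-peptide. Delivery method is not among them.

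The SAP text leaves this unchanged. Its section 14 adds education and prior severe hypoglycemia to the interaction list, but not delivery method. The sentence in SAP 6.2 that begins "The primary analysis described below will include a pre" goes on to promise a list of covariates fixed in advance, but SAP 7.2 names only site, with baseline handled through a common baseline mean.

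**The concern.** Two separate subgroup analyses invite a comparison of their p-values. If one is significant and the other is not, readers will tend to conclude that CGM works with one delivery method and not the other. That inference needs a direct estimate of the difference between the two effects, and the plan gives none for the one factor that helped to set its sample size.

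The protocol's guard is the caution in 10.17, which applies when the overall result is not significant. With 98% stated power, that condition will seldom be met under the planning assumptions. The caution is therefore silent in the very case where the overall result is positive and the subgroups disagree.

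A lesser matter is the primary estimate. Balance on delivery method is left to chance, and a variable that is already collected could take up any imbalance and some residual variance.

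**Working it through.** **Inputs (Protocol 10.3 and 4.4).** "type 1 error rate of 5% (2-tailed"); control mean from "the lower end of the BGM group estimate at 26-weeks (6"%); "treatment effect is a 50% reduction in the time spent <70 mg/dL and the effective standard deviation is 5"%; participants "randomized to one of two treatment groups in a 1:1 allocation". The planned difference is 0.5 x 6 = 3 percentage points, SD 5.

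**1. The plan's own figures.** A two-sample t-test with difference 3, SD 5 and two-sided 5% needs 120 in total for 90% power and 90 for 80%. With 180 completers, power is 98.1% by the normal formula and 97.9% by the t-test. All three stated figures (120, 90, 98%) reproduce.

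**2. Discordant subgroups under one common effect.** The two subgroups contain different people, so their tests are treated as independent.
- P(exactly one significant) = p1(1 - p2) + p2(1 - p1).
- Equal split, 90 each, power 0.80: 2 x 0.80 x 0.20 = 0.32.
- A 40:60 split of 180 completers gives 72 and 108, with power about 0.709 and 0.871: 0.709 x 0.129 + 0.871 x 0.291 = 0.091 + 0.253 = 0.345.

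So about one trial in three would show an apparent difference that is not there. The 0.80 is before multiplicity adjustment. Lower power does not help: at 0.70 in each the figure is 2 x 0.70 x 0.30 = 0.42.

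**3. What an interaction estimate would deliver.**
- Standard error of the treatment difference in a subgroup of 90: sqrt(4 x 25/90) = 1.05.
- Standard error of the difference between two such effects: sqrt(2 x 4 x 25/90) = 1.49.
- Half-width of the 95% interval: 1.96 x 1.49 = 2.9 points.

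That is as wide as the planned effect. The test has limited power, so the interval matters more than the p-value.

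**4. Chance imbalance in delivery method.** The reference is the hypergeometric distribution with 200 randomised, 100 per arm, and method unconstrained.

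| Pump users in total | P(difference in share above 10 points) | P(10 points or more) |
|---|---|---|
| 100 | 12.0% | 20.3% |
| 80 | 11.2% | 19.4% |

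**5. Effect on the primary estimate.** Shift = imbalance x gap between pump and injection users after baseline adjustment. The documents give no such gap; 0.5 to 2 points is an assumption. At a 10-point imbalance the shift is 0.10 x 0.5 = 0.05 to 0.10 x 2 = 0.2 points. The standard error of the primary difference is sqrt(4 x 25/180) = 0.75, so even 0.2 is about 0.27 of a standard error.

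**6. Price and gain of the covariate.** With 180 completers, one fewer residual degree of freedom leaves power at 97.9% if method explains nothing. If it explains 2%, 5% or 10% of residual variance (assumed), power is 98.1%, 98.4% or 98.8%. The required sample size does not rise.

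**The case against.** The strongest reply is that nothing here is an error. Site-stratified 1:1 randomisation, analysed with baseline and site, gives a valid test. Chance imbalance is already part of the standard error, and no principle requires a factor with a recruitment quota to be a covariate. Baseline time below 70 mg/dL is in the model and absorbs whatever pump-injection difference it carries. Protocol 10.6 also plans a sensitivity analysis for imbalanced factors, 10.1 describes the chapter as a framework, and the subgroup work is labelled exploratory.

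Most of this stands. A reader might infer that leaving method out of stratification or the model biases the primary result; the documents do not support that. Nor is the 10.6 sensitivity analysis unplanned: the analysis is pre-specified, and only the choice of factors waits on the data. A large gain in precision cannot be claimed either, because it would need a pump-injection gap that no section reports. Stratifying by method as well would also be a real trade-off. Protocol 1.3 implies at least 14 sites, hence at least 28 strata, or about 7 participants each or fewer.

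The reply does not reach the interaction point. The separate analyses do use delivery method, but they do not estimate the difference between the two effects. The framework clause does not help either, since 10.14 sets out an explicit list and the SAP text extends it without adding method. The exploratory label limits how strongly a difference may be claimed; it does not supply the estimate on which a claim should rest.

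**Conclusion.** The point holds as an interpretation and efficiency weakness, not as a validity error. Its main part is the missing treatment-by-method interaction. Under the plan's own 80% power per subgroup and a common true effect, discordant subgroup results arise about 32% of the time (about 34% at a 40:60 mix), with no planned estimate to set against them. This rests on the planning effect and SD applying equally in both subgroups and on unadjusted 5% tests.

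The covariate part is minor. An imbalance above 10 points has about a 12% chance (about 20% for 10 points or more). A 10-point imbalance shifts the estimate by 0.05 to 0.2 points against 3, given the assumed gap, and power stays near 98% either way. The covariate does nothing inside the pump-only and injection-only analyses, where it is constant.

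**What to change.** 1. **Protocol 10.14 (and SAP 14):** add baseline insulin delivery method, pump or injections, to the interaction list.
2. **Protocol 10.17 (and SAP 17.2):** state that any claim of a pump-injection difference rests on the interaction estimate and its 95% confidence interval, not on the two separate p-values, and that a non-significant interaction does not show equal effects.
3. **Protocol 10.6:** add baseline delivery method as a pre-specified fixed covariate in the linear model. If the longitudinal model of SAP 7.2 is used, with baseline as an outcome, add method and method-by-time; a main effect alone would force the same gap at both times. Reconcile SAP 6.2 with 7.2 by writing out the covariate list.

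Randomisation in 4.4 stays as it is. The variable is already collected and no participants are added. The cost is a few sentences, one model term in 10.6 (two in the longitudinal version) and one added interaction analysis, settled before comparative outcome data are examined. Label: free improvement.

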 7. Hypoglycemia Fear Survey (HFS-II) (32): The Hypoglycemia Fear Survey measures several dimensions of fear of hypoglycemia among adults with type 1 diabetes. It consists of a 10-item
- Behavior subscale that measured behaviors involved in avoidance and over-treatment of
- hypoglycemia and a 13-item Worry subscale that measures anxiety and fear surrounding
 hypoglycemia, each with a 5-choice Likert response format. Administration time is approximately 10
 minutes.
- 8. Diabetes Distress Scale (DDS) (33): 28-item questionnaire used to measure diabetes-related concerns
 about powerlessness, management, hypoglycemia, social perceptions, eating, physician, and
 friends/family.
- 9. Glucose Monitoring System Satisfaction Survey (GMSS) (34): 15-item questionnaire used to assess glucose monitoring device-related treatment satisfaction and QOL that is appropriate for use with both CGM and SMBG (validated subscales in T1D include Openness, Emotional Burden, Behavioral Burden and Trust)
- 10. Patient-Reported Outcomes Measurement Information System (PROMIS) Global Health Short Form
 (35): 10-item measure of overall QOL that covers both physical and mental health (PROMIS; see
 www.nihpromis.org; can be used to generate an equivalent EQ-5D-5L score for use in utility
 analyses.)
- 11. NIH Toolbox Cognition Battery (NIHTB-CB, www.nihtoolbox.org) a ~30 minute computerized
 battery of neuropsychological tests with nationally representative normative data for ages 3-85.
 Cognitive domains assessed include executive functioning, attention, episodic memory, language,
- processing speed and working memory. In addition to individual measure scores, a Cognitive
 Function Composite Score, Fluid Cognition Composite Score and Crystallized Cognition Composite
 Score are also generated by the program.
- 12. NIH Toolbox Emotion Battery (NIHTB-EB, www.nihtoolbox.org) $-a \sim 10$ minute battery of
- computer adaptive measures of emotional function; the following selected measures within the
- following domains will be administered: Psychological Well Being (positive affect survey), Stress &
- Self-Efficacy (perceived stress survey and self-efficacy survey), Social Relationships (instrumental
 support survey and emotional support survey), and Negative Affect (fear-affect survey and sadness
 survey).
- 13. Cost Utility questionnaires including the EuroQol EQ-5D-5L-5L and Optum SF-12V2v2 health
 utility instruments. Each are approximately 5-minute computer administered surveys assessing
 participants' current health status in specific dimensions such as mobility, pain, social functioning,

- and ability to self-care. They are also validated as norm-based standard measures for conversion into
- 801 a unidimensional preference measure of overall health status, for use in health utility assessments.
- 802 Such preference-based health measures are required to support the calculation of health-related costs 803 and benefits for the cost utility analysis.

805

CHAPTER 8: ADVERSE EVENTS AND RISKS

808 **8.1 Definition**

- 809 Reportable adverse events will include the following: severe hypoglycemia as defined below,
- 810 hyperglycemia/diabetic ketoacidosis (DKA) as defined below, all device-related events with potential
- 811 impact on participant safety, all falls or fractures, emergency room visits, and all events meeting criteria
- 812 for a serious adverse event. Skin reactions from sensor placement are only reportable if severe and/or 813 required treatment.
- 813

807

- 815 Hypoglycemic events are recorded as Adverse Events only if the event required assistance of another 816 person due to altered consciousness, and required another person to actively administer carbohydrate,
- glucagon, or other resuscitative actions. This means that the participant was impaired cognitively to the
- point that he/she was unable to treat himself/herself, was unable to verbalize his/ her needs, was
- incoherent, disoriented, and/or combative, or experienced seizure or coma. These episodes may be
- 820 associated with sufficient neuroglycopenia to induce seizure or coma. If plasma glucose measurements
- are not available during such an event, neurological recovery attributable to the restoration of plasma
- glucose to normal is considered sufficient evidence that the event was induced by a low plasma glucose concentration.
- 824

828

829

830

831

Hyperglycemic events are recorded as Adverse Events if evaluation or treatment was obtained from a
health care provider or if the event involved DKA, as defined by the Diabetes Control and Complications
Trial (DCCT), and had all of the following:

- Symptoms such as polyuria, polydipsia, nausea, or vomiting;
- Serum ketones >1.5 mmol/L or large/moderate urine ketones;
- Either arterial blood pH <7.30 or venous pH <7.24 or serum bicarbonate <15; and
- Treatment provided in a health care facility

In addition, hyperglycemia not meeting the definition of DKA will be reported as an adverse event if
emergency evaluation or treatment was obtained at a health care facility; these events are considered
Adverse Events and not Serious Adverse Events (SAE) unless one of the criteria for SAE is met.

835

836 8.2 Recording of Adverse Events

Throughout the course of the study, all efforts will be made to remain alert to possible adverse events or
untoward findings. The first concern will be the safety of the study participant, and appropriate medical
intervention will be made.

840

All reportable adverse events whether volunteered by the participant, discovered by study personnel during questioning, or detected through physical examination, laboratory test, or other means will be reported on an adverse event form online. Each adverse event form is reviewed by the Medical Monitor at the Coordinating Center to verify the coding and the reporting that is required.

845

The study investigator will assess the relationship of any adverse event to be related or unrelated by determining if there is a reasonable possibility that the adverse event may have been caused by the study intervention. To ensure consistency of adverse event causality assessments, investigators should apply the following general guideline when determining whether an adverse event is related:

850

851 Yes

- 852 There is a plausible temporal relationship between the onset of the adverse event and the study
- 853 intervention, and the adverse event cannot be readily explained by the participant's clinical state,
- 854 intercurrent illness, or concomitant therapies; and/or the adverse event follows a known pattern of

- response to the study intervention; and/or the adverse event abates or resolves upon discontinuation of the
- study intervention or dose reduction and, if applicable, reappears upon re-challenge.
- 857

- 858 No
- Evidence exists that the adverse event has an etiology other than the study intervention (e.g., pre-existing
 medical condition, underlying disease, intercurrent illness, or concomitant medication); and/or the adverse
 event has no plausible temporal relationship to study intervention.
- The intensity of adverse events will be rated on a three-point scale: (1) mild, (2) moderate, or (3) severe. It is emphasized that the term severe is a measure of intensity: thus, a severe adverse event is not necessarily serious. For example, itching for several days may be rated as severe, but may not be clinically serious.
- 867
- 868 Adverse events will be coded using the MedDRA dictionary.
- 869
- R69
- Adverse events that continue after the study participant's discontinuation or completion of the study will
 be followed until their medical outcome is determined or until no further change in the condition is
 expected.
- 873

874 8.3 Reporting Serious Adverse Events and Unexpected Adverse Device Events

- 875 A serious adverse event is any untoward occurrence that:
- Results in death.
- Is life-threatening (a non-life-threatening event which, had it been more severe, might have become
 life-threatening, is not necessarily considered a serious adverse event).
- Requires inpatient hospitalization or prolongation of existing hospitalization.
- Results in persistent or significant disability/incapacity or substantial disruption of the ability to conduct normal life functions (sight threatening).
- Is a congenital anomaly or birth defect.
- Is considered a significant medical event by the investigator based on medical judgment (e.g., may jeopardize the participant or may require medical/surgical intervention to prevent one of the outcomes listed above).
- An *Unanticipated Adverse Device Event* is defined as an adverse event caused by, or associated with, a device, if that effect or problem was not previously identified in nature, severity, or degree of incidence.
- 889
 890 Serious or unexpected device-related adverse events must be reported to the Coordinating Center within
 24 hours via completion of the online serious adverse event form.
- 892
 893 Other reportable adverse events and device malfunctions (with or without an adverse event) will be
 894 reported within 3 days of the investigator becoming aware of the event by completion of an electronic
 895 case report form.
- 896

- Bevice complaints not associated with device malfunction or an adverse event must be reported within 7
 days of the investigator becoming aware of the event.
- 899
- 900 The Coordinating Center will notify all participating investigators of any adverse event that is serious, 901 related, and unexpected. Notification will be made within 10 days after the Coordinating Center becomes 902 aware of the event.
- 902 903

- Each principal investigator is responsible for reporting serious study-related adverse events and abiding
- by any other reporting requirements specific to their institution.

907 8.4 Reportable Device Issues

- All adverse device effects, device complaints, and device malfunctions will be reported irrespective of whether an adverse event occurred, except in the following circumstances.
- 910
- 911 The following device issues are anticipated and will not be reported on a Device Issue Form but will 912 reported as an Adverse Event if the criteria for AE reporting described above are met:
- 913 Component disconnections
- CGM sensors lasting fewer than 7 days
- CGM tape adherence issues
- Battery lifespan deficiency due to inadequate charging or extensive wireless communication
- 917
 Intermittent device component disconnections/communication failures not leading to system replacement
- Device issues clearly addressed in the user guide manual that do not require additional troubleshooting
- Skin reactions from CGM sensor placement that don't meet criteria for AE reporting
- 922

923 8.5 Data and Safety Monitoring Board

A Data and Safety Monitoring Board (DSMB) will provide independent monitoring of the study protocol including adverse events and device issues with potential impact on participant safety. Cumulative adverse event data will be semi-annually tabulated for review by the DSMB. Following each DSMB data review, a summary will be made available for submission to Institutional Review Boards. A list of specific adverse events to be reported to the DSMB expeditiously will be compiled and included as part of the DSMB Standard Operating Procedures.

931 8.6 Risks and Discomforts

932 8.6.1 CGM Sensor Inaccuracy

There is a small risk of using CGM for insulin dosing, without a confirmatory BGM measurement, due to the accuracy of the sensor and the possibility of an adverse event if the CGM glucose value substantially deviates from the true glucose level, particularly when an insulin bolus is given. This risk has been mitigated by advising participants to check the blood glucose when symptoms or expectations do not match the CGM reading.

938

939 8.6.2 Skin Reactions

- 940 There is a low risk for developing a local skin infection at the site of the sensor needle placement.
- 941 Itchiness, redness, bleeding, and bruising at the insertion site may occur as well as local tape allergies.
- 942 Sensors may fracture in situ on rare occasions. In the rare instances when this has occurred in the past,
- 943 consulting physicians and surgeons have recommended not to remove the wire fragment from beneath the
- skin as long as there are no symptoms of infection or inflammation. In the event that signs and/or
- 945 symptoms of infection or inflammation arise such as redness, swelling, and pain subjects should consult
- 946 with the investigator or prescribing physician for the best course of action. If there is no portion of the 947 broken sensor wire fragment visible above the skin, attempts to remove it without medical mildered and
- 947 broken sensor wire fragment visible above the skin, attempts to remove it without medical guidance are 948 not advised.
- 948 949

- 950
- 951 During each follow-up visit, each site where a CGM sensor has been worn will be assessed by study
- personnel. Both acute and non-acute changes will be assessed (as described on the case report form and
- 953 in the Procedures Manual). If a skin reaction is classified as severe (the observation is extremely
- 954 noticeable and bothersome to participant and may indicate infection or risk of infection or potentially life-
- threatening allergic reaction) an Adverse Event Form will be completed.
- 956

957 8.6.3 Fingerstick Blood Glucose Measurements

- 958 Fingersticks may produce pain and/or ecchymosis at the site.
- 959

960 8.6.4 Psychosocial Questionnaires

- As part of the study, participants and parents will complete psychosocial questionnaires which include questions about their private attitudes, feelings and behavior related to diabetes. It is possible that some people may find these questionnaires to be mildly upsetting. Similar questionnaires have been used in previous research and these types of reactions have been uncommon.
- 965
- 966 The study may include other risks that are unknown at this time.
- 967 968

WISDM Protocol V3.2 4-16-18 clean

CHAPTER 9: MISCELLANEOUS CONSIDERATIONS

971 9.1 Benefits

It is expected that CGM devices will have an important role in the management of diabetes in olderadults. Therefore, the results of this study are likely to be beneficial for patients with diabetes.

974

969

970

975 It is possible that participants will not directly benefit from being a part of this study. However, it is also 976 possible that the blood glucose information from the monitor along with the information and instructions 977 provided for management decisions will be useful for participants' diabetes self-management.

978

979 9.2 Participant Reimbursement

980 The study will provide the CGM and related supplies, for the randomized trial. Eligible study participant 981 will also be provided a blood glucose meter and test strips. The study will provide the CGM and sensors 982 for the extension study. Participants will be able to use the BGM from the RCT trial for the extension 983 phase; however, test strips will not be provided for the extension portion of the study.

984

Participants will be provided with a reimbursement of \$50 (which may be in the form of a gift card) for
each completed protocol-required visit to help compensate for travel and other visit-related expenses.
Participants randomized to the BGM Group will be provided a reimbursement of \$25 for blinded sensor
placement visits to help compensate for travel and other visit-related expenses. Additional travel
expenses will be paid in select cases for participants with higher expenses. There will be no
compensation for completing telephone calls or unscheduled visits.

991

Participants who complete the study will be able to keep the study BGM and CGM devices, assuming that
commercially-available devices were used and the devices are functioning at the end of the study. Test
strips for the BGM and sensors for the CGM to be used after the study will be the participant's
responsibility.

996

997 9.3 Participant Withdrawal

Participation in the study is voluntary, and a participant may withdraw at any time. Participants who
discontinue using the study device should not be withdrawn and should continue study follow-up unless
the participant requests to withdraw from the study.

1001

1002 9.4 Confidentiality

